6.5 CONCOMITANT THERAPY

Any medication or vaccine (including over-the-counter or prescription medicines, vitamins, and/or herbal supplements) that the participant is receiving from the time of signature of the ICF through the Safety Follow-Up Call or Visit will be recorded in the eCRF along with:

- Reason for use
- Dates of administration including start and end dates
- Dosage information including dose and frequency

Permitted concomitant therapy

Participants taking medication routinely for a pre-existing condition should be on a treatment regimen that has been stable for at least 3 weeks prior to enrollment, and dosage changes should not be anticipated during the observation period for this study. Pre-study stable NSAID doses below the maximum dose specified in the local prescribing information at the time of enrollment are permitted. All concurrent prescription and nonprescription medications including over-the-counter and alternative preparations (including herbal remedies, vitamins, and health food supplements) should be recorded from the time of signature of the ICF throughout the treatment and follow-up periods.

Prohibited concomitant therapy

No premedication for pain or pyrexia relief is to be given for administration of BIVV001. Should pre-medications be contemplated, this will be discussed on a case-by-case basis with the Sanofi Study Medical Monitor or designee and before administration.

Medications prohibited during the study include:

1. NSAIDs at doses above the maximum dose specified in local prescribing information.
2. Acetylsalicylic acid (ASA) or other non-NSAIDs anti-platelet therapies.
3. Systemic treatment with chemotherapy and/or other immunosuppressive drugs (except for the treatment of HCV or HIV). The use of systemic steroids for the treatment of acute respiratory illness (eg, asthma), acute allergic episodes, or otherwise life-threatening episodes is allowed. Treatment in these circumstances should not exceed a 14-day duration. Local, topical, and/or inhaled steroid use is permitted.
4. Any other FVIII product.
5. Emicizumab.
6. Anticoagulant agents, excluding the use of heparin for intermittent flushing for maintenance of patency of intravenous catheters, and short-term thromboembolic prophylaxis during immobilization and/or perioperatively.

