8.1.2 Bleeding episodes data

In this study, a standardized definition of a bleeding episode based on International Society on Thrombosis and Haemostasis (ISTH) criteria will be used ([43](#)). A bleeding episode is defined as an episode that starts from the first sign of bleeding and ends no more than 72 hours after the last injection to treat the bleeding episode. Any subsequent bleeding at the same location and injections administered ≤ 72 hours from the previous injection will be considered as the same bleeding episode. Multiple bleeding locations treated with a single injection will also be considered a single bleeding episode. Any injection to treat the bleeding episode that is administered >72 hours after the preceding one will be considered the first injection to treat a new bleeding episode in the same location. Any injection used to treat subsequent bleeding at a different location will be considered a separate bleeding episode, regardless of the time from the last injection to treat a bleeding episode.

If a bleeding episode occurs on the same day as a regularly scheduled prophylaxis dose, participants are instructed to record in their diary:

- Treatment for bleeding episode: if the bleeding episode required BIVV001 treatment on the regular prophylaxis day.
- Follow up injection: if an additional injection is required to treat the bleed on the regular prophylaxis day.

OR

- Prophylaxis dose: if the bleeding episode did not require BIVV001 treatment on the regular prophylaxis day. In this case, the bleeding episode should be recorded and considered as an untreated bleeding episode.

Bleeding episodes or hemorrhages will be classified as either spontaneous or traumatic. The participant's ePD will serve as the primary source document for bleeding episodes while the participant is enrolled in the study. Spontaneous and traumatic bleeding episodes are further defined as follows:

- Spontaneous bleeding episodes: Bleeding episodes are classified as spontaneous if a participant or caregiver records a bleeding episode when there is no known contributing factor, such as a definite trauma or antecedent "strenuous" activity. The determination of "strenuous" is at the discretion of the Investigator, and the parent/caregiver/participant needs to be instructed by the Investigator on the proper categorization.

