8.1.4 Physician's global assessment (PGA)

The Physician's global assessment (PGA) is an assessment of the participant's response to treatment using a 4-point response scale (Table 9).

Table 9 - Physician's global assessment

Excellent	
 • Bleeding episodes responded to fewer than or the usual number of injections or less than or the usual dose of FVIII, OR • The rate of breakthrough bleeding during prophylaxis was less than or equal to that usually observed.
Effective	
 • Most bleeding episodes responded to the same number of injections and dose, but some required more injections or higher doses, OR • There was a minor increase in the rate of breakthrough bleeding.
Partially effective	
 • Bleeding episodes most often required more injections and/or higher doses than expected, OR • Adequate breakthrough bleeding prevention during prophylaxis required more frequent injections and/or higher doses.
Ineffective	
 • Routine failure to control hemostasis or hemostatic control required additional agents.

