4.2 PARTICIPANT DISPOSITIONS

Disposition of participants will be summarized using the All-Enrolled Analysis Set. The number (%) of participants included in each of the analysis populations listed in Table 3 will be summarized by age cohort and overall. The number of participants who completed the study and the number of participants who discontinued from the study early, including the primary reason for discontinuation, will be tabulated by age cohort and overall.

Separate summaries of enrollment by country/region and site and the number of participants attending each visit will be provided using the All-Enrolled Analysis Set by age cohort and overall. Disposition, including date of last visit and reason for early discontinuation, for participants who did not complete the study, will be provided in a listing by participant using the All-Enrolled Analysis Set.

Protocol deviations

The number of participants with major protocol deviations will be summarized by age cohort and overall for the FAS. Major protocol deviations that occurred during a major surgical/rehabilitation period will be presented separately in the summary.

Important protocol deviations impacting efficacy assessment will be identified by the study team from the following protocol deviation categories and will be finalized before the database lock:

- Entered the study even though entry criteria were not satisfied
- Developed withdrawal criteria during the study but were not withdrawn
- Received the wrong treatment or incorrect dose
- Received an excluded concomitant treatment
- Persistent misuse of the ePD device impacting interpretation of data based on medical review

Important protocol deviations will be summarized by age cohort and overall for the FAS. Participants who have at least one important protocol deviation will be excluded from the Per Protocol Set.

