A bleeding episode is counted in the analysis if it was treated with BIVV001. All types of bleeding episodes (spontaneous, traumatic, and type unknown) will be included in determining the annualized number.

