4.4.1.2 Main analytical approach

The mean and 95% CI of ABR will be estimated using a Negative-Binomial model. The model will include number of treated bleeding episodes during the efficacy period as response variable, log-transformed duration of efficacy period as offset variable to account for variable duration. Individual ABR will also be calculated for each participant and summarized descriptively. The summaries will be presented by age cohort and overall for the FAS.

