4.4.1.3 Sensitivity analyses

Sensitivity analysis of the ABR will also be performed using the Per Protocol Set, as well as using the FAS including participants with an efficacy period of at least 26 weeks.

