4.4.3 ABR based on all bleeding episodes

ABR will be summarized for all bleeds (treated and untreated) by age cohort and overall. All types of bleeding episodes (spontaneous, traumatic, and unknown) will be included, regardless of whether treatment was used or not. The estimated mean ABR and the corresponding 95% CI will be provided, using the same method as described in Section 4.4.1.2.

Definition of a bleeding episode (based on all bleeds)

The definition of all bleeds will follow the ISTH criteria, accounting for both treated and untreated bleeds, based on the date and time of the bleed as follows:

In the analysis of all bleeds, a bleeding episode starts from the first sign of a bleed (treated and untreated) and ends no more than 72 hours after the last injection to treat the bleed or the last untreated bleed at the same location, within which any sign of bleeding (treated and untreated) at the same location, injections \leq 72 hours apart, are considered the same bleeding episode.

Any injection or untreated bleed, occurring >72 hours after the preceding one, will be considered the start of a new bleeding episode. Any subsequent injection or untreated bleed at a different location will be considered a separate bleeding episode, regardless of the time from the last injection or bleed.

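### A bleed treated solely with a product other than BIVV001 is left out of the treated-bleed ABR, while its follow-up time stays in the denominator

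*SAP*

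**What the plan says.** The treated-bleed ABR is a secondary endpoint. SAP 4.4.1.1 states: "A bleeding episode is counted in the analysis if it was treated with BIVV001". That count is the numerator of each participant's ABR. It also feeds the negative binomial model in SAP 4.4.1.2: "The model will include number of treated bleeding episodes during the efficacy period as response variable". Protocol 9.4.3 describes the same model and refers to treated bleeds without naming a product.

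The protocol comes closest to a product restriction in the diary instructions of 8.1.2. There, a bleed on a dosing day is logged as untreated "if the bleeding episode did not require BIVV001 treatment on the regular prophylaxis day". That instruction covers prophylaxis days only and does not deal with bleeds treated with something else.

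Protocol 6.5 prohibits "Any other FVIII product" and also emicizumab; bypassing agents and antifibrinolytics are not on that list. SAP 4.2 has a deviation category "Received an excluded concomitant treatment". The lowest grade of the physician's global assessment (Protocol 8.1.4) reads: "Routine failure to control hemostasis or hemostatic control required additional agents".

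SAP 4.4.3 gives a separate ABR for all bleeds, counted "regardless of whether treatment was used or not". SAP 4.4 bases every other bleeding endpoint on treated bleeds.

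**The concern.** Defining a treated bleed by the study product makes the count depend on which vial was used as well as on whether the child bled and needed treatment. If a child's bleed is managed only with another product, the treated-bleed ABR records zero events for it and keeps the child's time at risk. The omission favours the study drug every time; nothing in the rule can push the estimate up.

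The product restriction in the analysis is added by the SAP, since Protocol 9.4.3 does not contain it. At stake is the accuracy of the main descriptive efficacy figure and of the joint and location breakdowns that follow from it. A child whose only bleed was of this kind would be reported as free of treated bleeds.

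**Working it through.** The plan states no ABR assumption, power or ABR-based sample size (Protocol 9.1 and 9.2), so there is no figure to reproduce. The check has two parts.

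**1. Where such a bleed goes**

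- Numerator: SAP 4.4.1.1 counts bleeds treated with BIVV001, so a bleed treated solely with another product is not counted.
- Denominator: SAP 4.1.1.2 interrupts the efficacy period for PK sampling, for surgery and rehabilitation, and for gaps of more than 28 days between BIVV001 injections. Use of another product is not an interruption, so the days normally stay in.
- Treated-bleed results with no all-bleeds counterpart: ABR by type and location (4.4.2), the annualized joint bleeding rate (4.4.10, which follows 4.4.1) and the ABR subgroup analyses (4.4.1.4).
- Sensitivity analyses (4.4.1.3): "Sensitivity analysis of the ABR will also be performed using the Per Protocol Set", and in the FAS restricted to an efficacy period of at least 26 weeks. The first may drop the child, if the other product is judged an important deviation. The second filters on duration. Neither adds the bleed back.
- All-bleeds ABR (4.4.3): the bleed is counted, pooled with bleeds that received no treatment.

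**2. Size per bleed**

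Inputs: the SAP formula ABR = bleeds / efficacy-period days × 365.25; 50 or 65 participants (SAP 2); 52 weeks = 364 days, or 364 − 7 = 357 days after a 168-hour PK period. The number of affected bleeds is an assumption.

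For one child, one uncounted bleed changes the individual ABR by:

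- 364 days: 365.25 / 364 = 1.003
- 357 days: 365.25 / 357 = 1.023

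With equal follow-up, the negative binomial mean with only an intercept and the offset equals total bleeds / total time. For k uncounted bleeds among n children, the shift in mean ABR is k × 365.25 / (n × 364):

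| k | n = 65 | n = 50 |
|---|---|---|
| 1 | 0.015 | 0.020 |
| 3 | 0.046 | 0.060 |
| 5 | 0.077 | 0.100 |
| 10 | 0.154 | 0.201 |

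In relative terms, if a share s of treated bleeds received only another product, reported ABR = true ABR × (1 − s). With an assumed true ABR of 1.00, s = 1%, 5% and 10% give 0.99, 0.95 and 0.90. With an assumed 50 bleeds over 50 person-years, one omitted bleed is 1/50 = 2%.

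**The case against.** The strongest defence is that this will hardly ever happen and that the plan reports the bleed anyway. Protocol 6.1.3 directs that bleeds needing treatment receive BIVV001, and other FVIII is prohibited. The deviation category in SAP 4.2 is generic: the prohibited list also covers high-dose NSAIDs, aspirin, immunosuppressants and anticoagulants, so the category does not show that other-product bleeds are expected. The all-bleeds ABR sits beside the treated-bleed ABR under the same secondary objective and uses the same model. A bleed meeting a seriousness criterion is also reported as an SAE (Protocol 8.3.6). Nothing is tested, so no decision depends on the count. On the assumed 50 bleeds in 50 person-years, an exact Poisson 95% interval is about 37 to 66 bleeds (ABR 0.74 to 1.32), which dwarfs a 2% shift.

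Most of this stands, and it limits the point. What it does not do is correct the treated-bleed figure. The gap between the two ABRs mixes other-product bleeds with bleeds that received no treatment, so the reader cannot recover the missing ones, and the joint, location and subgroup results have no all-bleeds version. Random error being larger does not excuse a shift that always has the same sign and can be avoided.

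A reader might infer that any bleed for which another product was used is removed. The text does not support that: a bleed given BIVV001 together with, before or after another agent was still treated with BIVV001 and is counted. A reader might also infer that the bleed disappears from the efficacy results; SAP 4.4.3 keeps it. Nor do the documents show that such bleeds are frequent or typically emergencies.

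**Conclusion.** The point holds in a narrow form. A bleed within the efficacy period that was treated solely with a product other than BIVV001 is omitted from the treated-bleed ABR and its derived results, with its time retained, so those figures can only be biased downward. Each such bleed costs about 0.015 to 0.020 of mean ABR (65 to 50 participants). This rests on equal follow-up of 364 days and on reading the SAP sentence as the full definition of a treated bleed, since no other qualifying product is named.

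The total effect depends on a number the documents do not give, and it is probably small. Bleeds after the last BIVV001 dose fall outside the treatment period (SAP 4.1.1.1) whatever product was used. Those inside a gap of more than 28 days lose their time as well as their count. This is a minor correction to a secondary, descriptive endpoint, worth making because the rule can be settled before database lock.

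**What to change.** Amend SAP 4.4.1.1 so that, for the ABR endpoints, a bleed counts as treated if BIVV001 or any other FVIII or hemostatic product was given for it. Apply the same definition to the type and location, joint and subgroup analyses. List the qualifying product classes. Keep the BIVV001-only definition for number of injections, dose and response per bleed (SAP 4.4.5 to 4.4.7), where it is the right one.

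Identify these bleeds by linking the bleed records in the ePD and eCRF to the concomitant-medication records. Protocol 6.5 already collects reason, dates and dose, so no new data field is needed. It does not ask for clock times, the episode definition uses a 72-hour window, and SAP Appendix 2 does not impute partial medication dates. A simple date-based rule is therefore needed where times are missing, for example a start date from the day of bleed onset to three calendar days later (72/24 = 3). The rule should also say whether doses of the other product extend the episode.

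The cost is a short SAP rule, a little linkage programming and an ABR that may come out slightly less favourable. If no such bleed occurs, the result is unchanged.

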4.4.1.2 Main analytical approach

The mean and 95% CI of ABR will be estimated using a Negative-Binomial model. The model will include number of treated bleeding episodes during the efficacy period as response variable, log-transformed duration of efficacy period as offset variable to account for variable duration. Individual ABR will also be calculated for each participant and summarized descriptively. The summaries will be presented by age cohort and overall for the FAS.

4.4.1.3 Sensitivity analyses

Sensitivity analysis of the ABR will also be performed using the Per Protocol Set, as well as using the FAS including participants with an efficacy period of at least 26 weeks.

4.4.1.4 Subgroup analyses

To assess the homogeneity of the treatment effect across various subgroups, analyses of the ABR will be performed across the following subgroups (categories with fewer than 5 participants may be combined with other categories):

- By bleeding phenotype at Baseline (estimated bleeds in prior 12 months, 0, >0-5, >5-10, >10)
- By number of target joints (none present, ≤ median of number present, > median of number present)
- By dosing and dosing interval compliance (<80%, $\ge80\%$)

The estimated mean ABR and the corresponding 95% CI will be provided, for each subgroup, using the same method as applied to the primary analysis. Forest plots will be provided.

4.4.2 ABR by type and location

ABR will be summarized descriptively by type and location for the following subsets of treated bleeds:

- Type of bleeding (spontaneous, traumatic, unknown)
- Location of bleeding (joint, muscle, internal, skin/mucosa)
- Location and type of bleeding (joint spontaneous, joint traumatic, muscle spontaneous, muscle traumatic, internal spontaneous, internal traumatic, skin/mucosa spontaneous, skin/mucosa traumatic)

The estimated mean ABR and the corresponding 95% CI will be provided, for each subset, using the same method as specified above. These tables will be presented by age cohort and overall for the FAS.

As a description of the raw data collected in this study, the unadjusted number of bleeding episodes per participant will be summarized using categorical (0, 1, 2, 3, 4, 5, and >5) and descriptive statistics overall and by bleed type (spontaneous, traumatic, unknown). The number

and percentage of participants experiencing a bleeding episode will be summarized categorically overall and by type of bleed (spontaneous, traumatic, unknown) as well as by bleed location (joint, muscle, internal, skin/mucosa, and unknown) for each bleed type; percentages will be based on the number of participants with an efficacy period. The total participant years followed during the efficacy period will be provided in order to put the un-annualized numbers in perspective.

4.4.3 ABR based on all bleeding episodes

ABR will be summarized for all bleeds (treated and untreated) by age cohort and overall. All types of bleeding episodes (spontaneous, traumatic, and unknown) will be included, regardless of whether treatment was used or not. The estimated mean ABR and the corresponding 95% CI will be provided, using the same method as described in Section 4.4.1.2.

Definition of a bleeding episode (based on all bleeds)

The definition of all bleeds will follow the ISTH criteria, accounting for both treated and untreated bleeds, based on the date and time of the bleed as follows:

In the analysis of all bleeds, a bleeding episode starts from the first sign of a bleed (treated and untreated) and ends no more than 72 hours after the last injection to treat the bleed or the last untreated bleed at the same location, within which any sign of bleeding (treated and untreated) at the same location, injections \leq 72 hours apart, are considered the same bleeding episode.

Any injection or untreated bleed, occurring >72 hours after the preceding one, will be considered the start of a new bleeding episode. Any subsequent injection or untreated bleed at a different location will be considered a separate bleeding episode, regardless of the time from the last injection or bleed.

4.4.4 Percentage of participants who maintain FVIII activity levels

The number and percentage of participants achieving steady-state trough FVIII activity levels above 1%, 3%, 5%, 10%, 15%, and 20% will be summarized by age cohort and overall. In these summaries, FVIII activity level will be based on the average trough samples (ie, nominal 168-hour time point) from each scheduled visit (Week 4, Week 13, Week 26, Week 39, Week 52) using the aPTT-based one-stage assay and chromogenic assay. Participants with trough samples that are outside 168 +/-5 hours from the previous dose will be excluded from this analysis.

